Pioglitazone for Idiopathic Gastroparesis NCT04300127 8/24/2020

Clinical Protocol Synopsis- Pioglitazone for the Treatment of Gastroparesis

Title

Pioglitazone for the Treatment of Idiopathic Gastroparesis (PIOGAS Study)

Type of study

• Open label pilot study

Objective

- The principal objective of this pilot study will be to evaluate whether 8 weeks of treatment of pioglitazone will improve symptoms as measured by the Gastrointestinal Symptom Index Daily Diary (GCSI-DD) in patients with Idiopathic Gastroparesis
- Secondary objectives of this study include:
 - To determine the effects of pioglitazone on other symptoms associated with gastroparesis using the Patient Assessment of Upper Gastrointestinal Symptom Severity Index (PAGI-SYM) and the Gastrointestinal Symptom Rating Scale (GSRS),
 - To determine the effects of pioglitazone on gastric emptying as measured by the ¹³C- Spirulina breath test,
 - To determine the effects of pioglitazone on satiety as measured by a liquid caloric test
 - To determine the effects of pioglitazone on depression and anxiety using the Beck Depression Inventory and State-Trait Anxiety Scores,
 - To determine the effects of pioglitazone on Quality of Life using the PAGI-QoL and SF-36 questionnaire,
 - To determine the effects of pioglitazone on markers of inflammation (CRP and ESR) and serum cytokine levels
 - And to determine the nature and incidence of adverse effects from a 12-week course of pioglitazone.

Treatment group

• Pioglitazone (30 mg po qd)

Population

 Age 18 years or older at registration with nausea, vomiting, and other symptoms suggestive of patients with chronic nausea and vomiting of presumed gastric origin, with symptomatic gastroparesis.

Study duration

- Up to 4 weeks of screening prior to pioglitazone treatment
- 8 weeks of treatment starting at initial dose of pioglitazone
- **4 weeks** of washout period
- Length of recruitment: 16 months

Sample size justification

- Total of **20 patients**
- Primary comparison: Baseline PAGI-SYM score versus 4, 8, and 12 weeks.

Number of clinical centers

- Johns Hopkins Bayview Medical Center.
- Mayo Clinic Scottsdale, Arizona This site will not perform enrollment of patients, It will only intervene as data analysis center under the supervision of [name].
- •

Inclusion criteria

- Age 18 years or older at registration

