- Diagnosis of gastroparesis as documented by gastric emptying scintigraphy (4-hour emptying after a low-fat meal with any combination of 2 and 4 hour retention of >60% and 10% respectively)
- Ongoing symptoms referable to gastroparesis (i.e. nausea and vomiting, bloating, and abdominal pain)
- Exclusion of other causes of symptoms such as mechanical gastrointestinal obstruction, uncontrolled esophagitis, peptic ulcer disease, etc. by standard radiographic or endoscopic tests
- Females will be required to use adequate contraceptive methods during study participation as determined by the Principal Investigator and the study team members

Exclusion criteria

- Another active disorder which could explain symptoms in the opinion of the investigator
- Age < than 18 years
- Pregnancy or nursing
- Previous surgery of the upper gastrointestinal tract including vagotomy
- Another active disorder which could explain symptoms in the opinion of the investigator
- Use of narcotics more than 3 days per week
- Significant hepatic injury as defined by significant alanine aminotransferase (ALT) and aspartate aminotransferase (AST) elevations of greater than 2xULN or a Child-Pugh score of 10 or greater
- Serious systemic disease, such as recent myocardial infarction/unstable angina, decompensated congestive heart failure, severe pulmonary disease with dyspnea at rest, or altered mental status from any cause
- Diabetes as defined by HbA1c >6.5 and/or fasting blood sugar of >125 mg/dL
- Contraindications to pioglitazone such as hypersensitivity or allergy
- Concurrent use of: estradiol, ethynyl estradiol, mestranol, pazopanib, warfarin, digoxin, atorvastatin, ranitidine, gemfibrozil, fexofenadine, midazolam
- Any other condition, which in the opinion of the investigator would impede compliance or hinder completion of the study
- History of bladder cancer or family history of bladder cancer
- Failure to give informed consent

Outcome measures

- **Primary:** The primary outcome measure is a binary (0,1) variable indicating improvement as measured by a decline of 1 or more in the total GCSI score
- Secondary outcome measures will be defined to address the following areas:
 - (1) Gastrointestinal symptoms
 - Subscores for the GCSI: nausea/vomiting, postprandial fullness, bloating
 - Total and Subscores for the GSRS
 NIH Patient Reported Outcome Measurement Information System (PROMIS)

gastrointestinal symptom scales.

- (2) Quality of Life
 - PAGI-QoL
 - SF-36

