- (3) Inflammatory Markers
 - CRP and ESR
- (4) Mood and Behavior
 - Beck Depression Inventory
 - State-Trait Anxiety
- (5) Adverse Events
 - Biochemical tests
 - Symptoms of cardiac or pulmonary disease
 - Any other AE reported or noted throughout the study and follow-up

Justification of sample size

This will be a pilot study recruiting 20 candidates.

Statistical analysis

All analyses will be on an intention-to-treat basis. Patients who do not have any of the decline of 1 or more in the total GCSI score recorded during the period of treatment will be counted as not improved (i.e., 0) for the primary outcome. Comparisons will also be made with baseline total GCSI score and other secondary outcomes. Numerical changes will be analyzed by descriptively comparing the between-treatment group differences in mean and median changes; P-values will be derived from Wilcoxon rank sum tests for comparison of the distribution of changes in each group The two-sided P-values so derived will be reported in the primary results paper of the trial. A two-sided P-value of 0.05 will be considered statistically significant.

Standard treatment recommendations

During the screening period, patients will receive a standardized set of recommendations to include dietary modification. The patient's medications are reviewed to eliminate drugs that might exacerbate the underlying dysmotility disorder or prevent the beneficial actions of a prokinetic agent. Dietary modification and use of pain medications as appropriate are the primary management approaches. If symptoms require further treatment during the trial, patients will be instructed to take rescue medications that they would usually take such as prochlorperazine for nausea and vomiting, and tramadol for abdominal pain. These recommendations have been prepared by the GpCRC Steering Committee as standard of care in the management of patients with gastroparesis or related disorders. This will help ensure that the patients in both treatment groups receive standard of care treatment.

Visit schedule

- Screening: at least 1 visit separated by at least 1 calendar day prior pioglitazone treatment; screening period can last no more than 4 weeks after registration
- Final pre-treatment interview, dispensing of study agent
- Follow-up visits: every 4 weeks after pioglitazone treatment throughout the 12 week study
- Post-treatment: follow-up at **16 weeks**

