- Patient Assessment of Upper Gastrointestinal Disorders-Quality of Life (PAGI-QoL): A validated 30 item questionnaire to assess quality of life in patients with dyspepsia, GERD, or gastroparesis. Copyright© 2004 Johnson & Johnson.
- State Trait Anxiety Inventory: The STAI is a 40-item self-report measure designed to assess both situational and characterological anxiety. This measure provides two subscale scores (State and Trait) and has been shown to exhibit good reliability and internal consistency.
- Beck Depression Inventory, Second Edition (BDI-II): The BDI-II is a commonly used, reliable 21-item self-report measure designated to assess for depression.

- Patient Assessment of Upper Gastrointestinal Disorders-Symptoms (PAGI-SYM): The self-reported questionnaire is composed of 20 items and 6 subscales. The severity of each symptom item over a 2-week recall period is scored from 0 (none or absent) to 5 (very severe). The GCSI, a 9-symptom survey relevant to gastroparesis stratified in 3 subscales – nausea/vomiting, fullness/early satiety, and bloating, is contained in the PAGI-SYM. The GCSI correlates with patient severity ratings and is responsive to changes in overall symptoms. Two additional items for constipation and diarrhea also will be recorded and scored and their main symptom will be determined.
- Gastrointestinal Symptom Rating Scale (GSRS): The GSRS is a disease-specific instrument of 15 items combined into five symptom clusters depicting Reflux, Abdominal pain, Indigestion, Diarrhea, and Constipation. The GSRS has a seven-point graded Likerttype scale where 1 represents absence of troublesome symptoms and 7 represents very troublesome symptoms. The reliability and validity of the GSRS are well-documented and norm values for a general population are available.
- PROMIS NIH Scale: The Patient-Reported Outcomes Measurement Information System (PROMIS®) GI Symptom item bank captures upper and lower GI symptoms (reflux, disrupted swallowing, nausea/vomiting, belly pain, gas /bloating /flatulence, diarrhea, constipation, and fecal incontinence).

Recruitment Procedures

Individuals Responsible for Approaching Participants:

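### One unadjusted 0.05 rule covers a primary comparison made at three visits and all secondary outcomes; on the primary comparison alone the false-positive risk is about 10% to 14%, not 5%

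*Combined protocol and SAP*

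**What the plan says.** Statistical analysis sets the threshold in one unqualified sentence: "A two-sided P-value of 0.05 will be considered statistically significant". The sentence before it sends the results to publication: "The two-sided P-values so derived will be reported in the primary results paper of the trial". The same paragraph extends the comparisons to total GCSI and the other secondary outcomes. Nowhere do the documents give a multiplicity adjustment, a testing order, or a statement that secondary P-values are exploratory.

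Three places describe what is primary, and they differ:

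- Sample size justification (synopsis): "Primary comparison: Baseline PAGI-SYM score versus 4, 8, and 12 weeks". This is PAGI-SYM at three visits.
- Outcome measures: "The primary outcome measure is a binary (0,1) variable indicating improvement as measured by a decline of 1 or more in the total GCSI score". This is one binary GCSI variable with no visit named. Statistical analysis gives it no reference rate and no test.
- Objective: symptom improvement on the GCSI-DD after 8 weeks of treatment.

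The secondary list is broad. It includes "Subscores for the GCSI: nausea/vomiting, postprandial fullness, bloating", the GSRS total and subscores, the PROMIS gastrointestinal scales, PAGI-QoL, SF-36, CRP and ESR, the Beck inventory and the anxiety inventory. Under Specific Tests and Questionnaires the PROMIS bank is described as covering "reflux, disrupted swallowing, nausea/vomiting, belly pain, gas /bloating /flatulence, diarrhea, constipation, and fecal incontinence", which is eight areas.

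**The concern.** A 0.05 threshold carries a 5% error rate only when it is attached to one test. Here it is attached to a primary comparison that is read three times and to a long unranked list of secondary scores. A reader of the results paper could not tell which significant result was the planned one.

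The conflict over the primary makes this worse. With two instruments, a binary and a numerical version, and no agreed visit, nothing in the plan prevents a result at one visit or on one subscore from being presented as the trial's finding.

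**Working it through.** **No plan figure to reproduce.** The documents state no familywise error rate and no number of tests. They also give no effect size, standard deviation, response rate or power behind the 20 patients.

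**Inputs.** Two-sided 0.05 per test (Statistical analysis). Follow-up at weeks 4, 8 and 12 (Follow-up visits and the Data Collection Schedule). The correlation between tests is not given, so it is an assumption, taken as equal for all pairs over a range from 0 to 0.8. The rank sum test named in the plan compares groups and the study has one group, so within-patient tests are assumed.

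**Count of tests (ours).**

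| Outcome | Low count | High count |
|---|---|---|
| PAGI-SYM or GCSI total | 1 | 3 (three visits) |
| GCSI subscores | 3 | 9 (3 × 3 visits) |
| GSRS total and five clusters | 6 | 6 (week 12 only) |
| PROMIS | 1 | 24 (8 × 3 visits) |
| SF-36 | 1 | 1 (assumed one score) |
| CRP, ESR | 2 | 2 (week 8) |
| Beck inventory | 1 | 1 (week 12) |
| Anxiety inventory | 1 | 2 (State, Trait) |
| Total | 16 | 48 |

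Both totals include the primary score. PAGI-QoL is left out because the Data Collection Schedule does not list it. Testing every score once, with PROMIS as 8 and the anxiety inventory as 2, gives 16 + 7 + 1 = 24.

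**Formulas.** For k independent tests, the chance of at least one false positive is 1 − 0.95^k:

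- k = 3: 1 − 0.95³ = 0.143
- k = 16: 1 − 0.95¹⁶ = 0.560
- k = 24: 1 − 0.95²⁴ = 0.708
- k = 48: 1 − 0.95⁴⁸ = 0.915

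With common correlation ρ and c = 1.96, it is 1 − ∫ [Φ((c − √ρ·x)/√(1−ρ)) − Φ((−c − √ρ·x)/√(1−ρ))]^k φ(x) dx:

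| ρ | k = 3 | k = 16 | k = 24 | k = 48 |
|---|---|---|---|---|
| 0 | 14.3% | 56.0% | 70.8% | 91.5% |
| 0.3 | 13.6% | 47.6% | 59.5% | 79.5% |
| 0.5 | 12.5% | 37.4% | 45.8% | 61.3% |
| 0.7 | 10.9% | 26.4% | 31.1% | 39.9% |
| 0.8 | 9.8% | 20.7% | 23.8% | 29.5% |

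The expected number of false positives does not depend on the correlation: 3 × 0.05 = 0.15, 16 × 0.05 = 0.8, 48 × 0.05 = 2.4.

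**Check at n = 20.** Simulated two-sided signed-rank tests (exact size 0.0484, 10,000 runs per setting) at ρ = 0, 0.3, 0.5 and 0.7 gave 14.4%, 13.3%, 12.4% and 11.7% for 3 tests, and 91.1%, 80.0%, 63.2% and 43.2% for 48. These agree closely with the normal model.

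**After the fix.** One pre-named test has an error of 5%. Three visits under Holm start at 0.05/3 = 0.0167. The Bonferroni bound for three independent tests is 1 − (1 − 0.0167)³ = 0.049.

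**The case against.** The strongest reply is that this is an "Open label pilot study" with outcomes already labelled primary and secondary, that mean and median changes are to be compared descriptively, and that Outcome measures names one primary variable, so three primary tests may never be run. Part of this stands. If the binary GCSI outcome is the primary, the three-visit inflation does not arise. But the plan gives that outcome no test, and the three-visit line is still in the synopsis. Pilot status would excuse unadjusted P-values that were labelled exploratory. The same paragraph instead gives them a significance threshold and a place in the primary paper.

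Stronger readings are tempting and should be resisted:

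- *A false significant result is likely.* For the three primary visits it is not: the risk is 10% to 14%. For the whole set it depends on a correlation the documents do not give. At 0.7 the chance is below even for every count considered. High correlation is plausible in places, since the GCSI sits inside PAGI-SYM and the GSRS total is tested beside its own clusters.
- *The plan contains 48 tests.* Half of them come from testing eight PROMIS areas separately at three visits, which no section says will be done.
- *The small sample is to blame.* "This will be a pilot study recruiting 20 candidates" describes the sample size. The error here is driven by the number of tests and their correlation, not by 20 patients.
- *A chance result could launch a controlled trial.* No section states a go or no-go rule, so this cannot be claimed.

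**Conclusion.** The point holds for the rule as written. An unadjusted 0.05 applied to the three-visit primary comparison gives a false-positive risk of about 10% (correlation 0.8) to 14% (independence), two to nearly three times the nominal 5%. Over all outcomes, with roughly 16 to 48 tests in total, the chance of at least one false significant result is 56% to 91% if independent, 37% to 61% at a correlation of 0.5, and 26% to 40% at 0.7.

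These figures rest on our count, an assumed common correlation, within-patient tests in place of the rank sum test, and no true change on any outcome. The primary-comparison figure also rests on the synopsis line, which Outcome measures and Objective contradict. Even at a correlation of 0.8, the risk over the whole set is 21% or more, so the need for a stated rule does not depend on the exact correlation.

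**What to change.** 1. Reconcile Sample size justification, Outcome measures and Objective so that they name one primary instrument and one form of it.
2. Reconcile the treatment-period statements before naming the primary visit. Study duration gives 8 weeks of treatment and 4 of washout, the last secondary objective refers to a 12-week course, and Visit schedule puts post-treatment follow-up at week 16. As it stands, it is unclear whether week 12 is on or off treatment.
3. In Statistical analysis, tie the 0.05 rule to one pre-named comparison (one instrument, one visit) with a test that suits a single group.
4. Report the other visits and all secondary outcomes as estimates with 95% confidence intervals, labelled exploratory, with no claim of statistical significance.
5. If all three visits are to stay primary, use Holm across them.

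The change needs no extra patients, visits or data. Steps 3 to 5 are a few sentences; steps 1 and 2 require decisions from the sponsor. The downside is that fewer results can be called significant.

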As part of the screening process for the PIOGAS trial, the patient must have a standardized 4-hour scintigraphic evaluation of gastric emptying using a low fat Egg Beaters meal that is available for review by the study physician. The standard of care gastric emptying scintigraphy may have been obtained at any time within 2 years prior to the registration date. Patients must also have a normal upper endoscopy within the last 2 years, to rule out other potential causes of symptoms such as mechanical obstruction, inflammatory or other structural lesions of the GI tract or non-gastrointestinal causes. Recording of screening data on trial forms may not start until the patient has signed the PIOGAS trial consent statement. Screening and baseline data collection procedures will include questionnaires, physical examination, various laboratory tests, clinical procedures on patients, and review of the patient's medical chart. Data abstracted from a patient's chart may include laboratory, endoscopy, scintigraphy, and radiology test results. Prior therapy will be reviewed and patients will be asked to stop specific treatments such as antiemetic medications. Baseline and follow up questionnaires can be answered through REDcap.

All participants who sign the consent statement will be registered in the trial database (REDcap). Each participant who starts screening will be accounted for at the end of screening, as either a screening success or a screening failure. A screening failure is defined and a participant who signed the consent form and was registered for the PIOGAS trial data system, but is found to be ineligible prior to start of treatment; screening failures include patients who meet medical eligibility criteria but change their mind and do not consent to participation in the trial. The reason for screening failure will be recorded and keyed in the trial database.

Screening visit: The patient should be in a fasting state (no food or drink after midnight the night before) for this visit. The patient will sign the consent form at or prior to the screening visit and will undergo a history and physical examination to identify other illness and contraindications for participation such as use of antiemetic medications.

In addition, the patient will be provided one week supplies of the Gastroparesis Cardinal Symptom index-Daily Diary (GCSI-DD) for completion each night before bed.

The patient will complete the following questionnaires:

- PAGI-SYM

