Anthropomorphic assessments (body weight, body height, body mass index [BMI], waist circumference, hip circumference, vital signs (systolic and diastolic blood pressure, heart rate, respiratory rate, body temperature); and general physical findings will be collected.

• Week 16 visit: This will be a terminal visit. Medical history including side effect or symptom profile, and include a questionnaire for global overall relief of symptoms question and clinical global patient impression question.

PIOGAS Study Data Collection Schedule								
	Screening & Pioglitazone treatment Visits		Follow-up Visits: Weeks from start of treatment					
	Screening	Treatment initiation	4	8	12			
Consent	Х							
Gastric emptying scintigraphy results review	Х							
Baseline medical history	Х							
GCSI-DD	Х		Х					

			N N		
Collection of GCSI-DD			Х	Х	Х
PAGI-SYM questionnaire	Х		Х	Х	Х
GSRS questionnaire	X				Х
SR-36v2 Healthy Survey questionnaire	Х				Х
Beck Depression Inventory-II	Х				Х
State Trait Anxiety Inventory	X				Х
PROMIS NIH scale	Х		Х	Х	Х
Physical exam	Х				Х
Study drug dispensed		Х			
Follow-up medical history, including			Х	Х	Х
review of adverse events					
CBC, CMP	Х			Х	
HbA1c	X				
CRP & ESR	Х			Х	
12-lead EKG	Х				
Pregnancy test	X				

Physical exam includes weight, vital signs (temperature, heart rate, blood pressure) and general physical findings **Complete blood count (CBC)**: white blood cells, red blood cells, hemoglobin, hematocrit, platelets **Complete metabolic panel (CMP)**: sodium, potassium, chloride, carbon dioxide, glucose, calcium, BUN, creatinine, bilirubin, ALT, AST, alkaline phosphatase, magnesium, albumin, total protein

Specific Tests and Questionnaires

- Laboratory Tests: All laboratory test results may be obtained as archival material from the patient's chart or should be collected as part of standard of care during screening. The etiologic tests required once as part of screening include: high-sensitivity C-reactive protein (hs-CRP); sedimentation rate (ESR); complete blood count (white blood cell count (WBC), red blood cell count (RBC), hemoglobin, hematocrit, platelet count); comprehensive metabolic panel (sodium, potassium, chloride, carbon dioxide, calcium, BUN, creatinine, glucose, and liver panel including total protein, albumin, total bilirubin, aspartate aminotransferase, alanine aminotransferase, alkaline phosphatase); and hemoglobin A1c.

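### Baseline is the only comparator but is not placed at the start of treatment, and the first on-treatment diary supply falls short of the nights collected at week 4

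*Combined protocol and SAP*

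**What the plan says.** The study is open label with one treatment group (Type of study; Treatment group).

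**What is compared.** The principal objective asks whether eight weeks of pioglitazone "will improve symptoms as measured by the Gastrointestinal Symptom Index Daily Diary (GCSI-DD) in patients with Idiopathic Gastroparesis". Sample size justification gives "Primary comparison: Baseline PAGI-SYM score versus 4, 8, and 12 weeks". Outcome measures defines the primary outcome as a fall of at least one point in total GCSI and names no baseline time point. Specific Tests and Questionnaires says that the GCSI "is contained in the PAGI-SYM" and, of the PAGI-SYM items, "The severity of each symptom item over a 2-week recall period is scored" from 0 to 5.

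**What happens in screening.** Visit schedule allows treatment to start from 1 calendar day after screening and caps screening at 4 weeks from registration. Standard treatment recommendations states: "During the screening period, patients will receive a standardized set of recommendations to include dietary modification". The same section has medications reviewed and some removed. Section (1), on screening and baseline data, adds that "patients will be asked to stop specific treatments such as antiemetic medications".

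**When baseline is measured.** Section (1) places the PAGI-SYM at the screening visit. In the Data Collection Schedule the row "PAGI-SYM questionnaire" is marked at screening and at weeks 4, 8 and 12, and is blank at treatment initiation. Section (2), Treatment Start Visit, lists no questionnaire. One week of diary forms is issued at the screening visit and collected at treatment start. No text says which seven nights they must cover.

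**On-treatment diary.** After the first dose the patient receives a supply whose length is misprinted (*thee* week). The week 4 visit collects the diary for every night from the start of treatment. Weeks 4 and 8 each issue a further 4 weeks of forms.

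**The concern.** With no control arm, whatever moves symptoms between the baseline window and follow-up goes into the result. Here the protocol itself schedules such movements: diet advice, removal of aggravating drugs and withdrawal of antiemetics. A PAGI-SYM completed at the screening visit looks back over the two weeks before it. It can therefore describe symptoms before those changes, while every follow-up score comes after them.

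The direction is not fixed. Better diet or removal of aggravating drugs could lower scores and be credited to pioglitazone. Stopping antiemetics could raise them and hide a benefit. The plan still intends two-sided P-values at 0.05 for the primary paper.

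The diary shortage is a separate matter. Under Statistical analysis, a patient with no qualifying fall recorded during treatment counts as not improved, so unrecorded nights before week 4 can matter if the diary supplies the GCSI.

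**Working it through.** The plan derives no figure here that could be reproduced: the 20 patients are stated without a calculation. The check is calendar arithmetic on the plan's own intervals.

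**Inputs.** PAGI-SYM recall 14 days (Specific Tests and Questionnaires). Screening 1 to 28 days (Visit schedule). Baseline diary 7 nights (Screening visit; Treatment Start Visit). Nights collected at week 4: 28 (Week 4 visit). Patients: 20.

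**Step 1: PAGI-SYM window.** Let *i* be the days from screening visit to first dose. The baseline window runs from day −(14 + *i*) to day −*i*. All 14 recall days precede the screening visit whatever *i* is. With a repeat at treatment start, the number preceding it is max(0, 14 − *i*).

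| *i* | Window now | Recall days before screening visit, now | With repeat at treatment start |
|---|---|---|---|
| 1 | −15 to −1 | 14/14 | 13/14 (93%) |
| 7 | −21 to −7 | 14/14 | 7/14 (50%) |
| 10 | −24 to −10 | 14/14 | 4/14 (29%) |
| 14 | −28 to −14 | 14/14 | 0/14 |
| 28 | −42 to −28 | 14/14 | 0/14 |

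The row *i* = 1 meets the Visit schedule minimum but cannot hold the one-week diary, so 7 days is the fastest workable case. The row *i* = 28 assumes that registration takes place at the screening visit. The counts show overlap with days before that visit. Overlap with days before the changes themselves depends on dates that the plan does not give.

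**Step 2: baseline diary.** If the diary is filled in directly after a screening visit 28 days before dosing, its last night is 28 − 7 = 21 days before first dose. If it is filled in during the last week, the gap is 0. At the 1-day minimum only 1 of the 7 nights can exist.

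**Step 3: diary supply.**
- Read as three weeks: 21/28 = 75% of nights supplied. Shortage 7 × 20 = 140 of 28 × 20 = 560 patient-nights (25%). To week 8: 140 of 56 × 20 = 1,120 (12.5%).
- Read as *the* week: 7/28 = 25% supplied. Shortage 21 × 20 = 420 of 560 (75%).
- Weeks 4–8 and 8–12: 28 of 28 nights each.

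**Step 4: scale, by assumption only.** The plan gives no SD and no expected shift. Suppose no drug effect, normal changes with SD 0.8 to 1.2, and an improvement *d* between the baseline window and dosing. Then P(fall ≥ 1) = Φ((−1 + *d*)/SD) at one time point. This gives 11–20% for *d* = 0, 17–27% for *d* = 0.25 and 27–34% for *d* = 0.5. A worsening of 0.25 gives 6–15%. A paired test of the mean change with n = 20 (normal approximation, two-sided 0.05) would reject in about 15–29% of trials at *d* = 0.25 and 46–80% at *d* = 0.5. These figures show sensitivity and do not estimate the bias in this trial.

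**The case against.** The strongest reply is that the principal objective names the diary and lists PAGI-SYM as secondary; only the line under Sample size justification makes PAGI-SYM primary. The diary is completed prospectively after the screening visit and handed in at treatment start, so it lacks only a rule fixing which nights count. That stands: on the diary reading the problem is smaller. It does not disappear, and the plan does not settle which reading applies.

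The extreme windows are scenarios. Consent may precede the screening visit, more than one screening visit is possible, and no typical interval is given. Many patients come from the study physicians' own rosters, so the advice may change little for them. All of this is fair, and it is why no size or sign is claimed. None of it places a PAGI-SYM at treatment start.

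The plan lets questionnaires be answered in REDCap, which might also cover the missing diary nights. But the diary is described as supplied and collected, and no electronic diary is specified. The misprint could be a typing slip, yet neither reading reaches 28 nights.

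On antiemetics, stopping regular use and allowing as-needed rescue could be compatible. The plan does not say so, and section (1) also lists "contraindications for participation such as use of antiemetic medications", which sits uneasily with asking users to stop.

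Finally, the absence of a control arm is the larger limitation, and the remedy is partial. Both are true. In an uncontrolled pilot that is a reason to make the one available comparator as clean as is cheaply possible.

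**Conclusion.** The concern holds, and the sponsor should change the plan. As written, the PAGI-SYM baseline describes the 14 days before the screening visit. That period ends 7 to 28 days before first dose in the workable range, while protocol-driven changes fall between baseline and follow-up in no fixed order. The diary baseline can end 0 to 21 days before first dose. The resulting bias has unknown size and sign, because the plan does not say how many patients change diet or medication, or when.

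The diary supply is short under either reading: 140 of 560 patient-nights to week 4 if three weeks, 420 of 560 if one. The nights leading to week 8, the end of the treatment period in the principal objective, are fully supplied.

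The conclusion rests on the screening visit being where the PAGI-SYM is completed, as section (1) and the schedule show, and on the diary being limited to the forms issued.

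**What to change.** 1. Define the baseline GCSI-DD as the 7 nights immediately before first dose. Align the 1-calendar-day minimum in Visit schedule with the one-week diary that the Treatment Start Visit already requires.
2. Repeat PAGI-SYM at the treatment-start visit, before first dose, and use it as the PAGI-SYM baseline. Keep the screening score for a sensitivity comparison.
3. Record the dates of diet and medication changes, so that any overlap with the 2-week recall is known.
4. Issue 28 nights of GCSI-DD at treatment start, to match what week 4 collects.
5. Reconcile the passages on stopping antiemetics, on antiemetic use as a contraindication, and on usual rescue medication for nausea and vomiting. No clinical rule or minimum period off medication is proposed here.

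**Cost.** One extra 20-item questionnaire per patient, which may be answered through REDCap, and 7 × 20 = 140 more diary forms. A patient whose first dose is postponed would have to repeat or extend the diary week. Neither more patients nor screening beyond the implied week is needed.

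**What remains.** When screening is shorter than 14 days, or the changes come late in it, part of the treatment-start recall may still precede them. Without a control arm the drug effect is still not isolated.
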